5.2.2.2 Adverse event collection and reporting

AEs collection

Upon enrolment into a trial, the subject's baseline condition is assessed (for instance, by documentation of medical history/concomitant diagnoses), and relevant changes from baseline are noted subsequently.

Subjects will be required to report spontaneously any AEs as well as the time of onset, end, and intensity of these events. In addition, each subject will be regularly assessed by the medical staff throughout the clinical trial and whenever the investigator deems necessary. As a minimum, subjects will be questioned for AEs (and concomitant therapies) at the time points indicated in the Flow Chart. Assessment will be made using non-specific questions such as 'How do you feel?'. Specific questions will be asked wherever necessary in order to more precisely describe an AE.

A carefully written record of all AEs shall be kept by the investigator in charge of the trial. Records of AEs shall include data on the time of onset, end time, intensity of the event, and any treatment or action required for the event and its outcome.

The following must be collected and documented on the appropriate CRF(s) by the investigator:

- From signing the informed consent onwards until an individual subject's end of trial:
 - o All AEs (serious and non-serious) and all AESIs
 - The only exception to this rule are AEs (serious and non-serious) and AESIs in Phase I trials in healthy volunteers, when subjects discontinue from the trial due to screening failures prior to administration of any trial medication. In these cases, the subjects' data must be collected at trial site but will not be entered in the CRF or trial database and will not be reported in the CTR.

Proprietary confidential information © 2018 Boehringer Ingelheim International GmbH or one or more of its affiliated companies

- After the individual subject's end of trial:
 - The investigator does not need to actively monitor the subject for AEs but should only report related SAEs and related AESIs of which the investigator may become aware of by any means of communication, e.g. phone call. Those AEs should, however, not be reported in the CRF.

AE reporting to sponsor and timelines

The Investigator must report SAEs, AESIs, and non-serious AEs which are relevant for the reported SAE or AESI, on the BI SAE form via fax immediately (within 24 hours) to the sponsor's unique entry point (country specific contact details will be provided in the ISF). The same timeline applies if follow-up information becomes available. In specific occasions the Investigator could inform the sponsor upfront via telephone. This does not replace the requirement to complete and fax the BI SAE form.

With receipt of any further information to these events, a follow-up SAE form has to be provided. For follow-up information, the same rules and timelines apply as for initial information.

Information required

All (S)AEs, including those persisting after the individual subject's end of trial, must be followed up until they have resolved, have been sufficiently assessed as 'chronic' or 'stable', or no further information can be obtained.

5.2.3 Assessment of safety laboratory parameters

For the assessment of laboratory parameters, blood and urine samples will be collected by the trial site at the time points indicated in the Flow Chart after the subjects have fasted for at least 8 h. Overnight fasting is not required at the discretion of the investigator or designee for retests.

The parameters that will be determined are listed in Tables 5.2.3: 1 and 5.2.3: 2. Reference ranges will be provided in the ISF, Section 10.

Manual differential white blood cell count or urine sediment examinations will only be performed if there is an abnormality in the automatic blood cell count or in the urinalysis, respectively.

c15848749-03

Page 50 of 84

Proprietary confidential information © 2018 Boehringer Ingelheim International GmbH or one or more of its affiliated companies

Table 5.2.3: 1 Routine laboratory tests

Category	Test name	A^1	B^2	C^3
Haematology	Haematocrit	X	X	X
	Haemoglobin	X	X	X
	Red blood cells (RBC)	X	X	X
	White blood cells (WBC)	X	X	X
	Platelets	X	X	X
	Reticulocyte count	X	X	X
Automatic WBC	Neutrophiles	X	X	X
differential	Eosinophils	X	X	X
(relative and absolute)	Basophils	X	X	X
,	Monocytes	X	X	X
	Lymphocytes	X	X	X
Manual differential	Polymorphnuclear neutrophils (segs), band			
WBC (if automatic	neutrophils (stabs), eosinophils, basophils,			
differential WBC is	monocytes, lymphocytes			
abnormal and clinically	monocytes, tymphocytes			
relevant in the opinion of				
the investigator) Coagulation	Activated partial thromboplastin time (aPTT)	X	X	X
Coagulation				
Г	Prothrombin Time (Quick and INR)	X	X	X
Enzymes	Aspartate aminotransferase (AST/GOT, SGOT)	X	X	X
	Alanine aminotransferase (ALT/GPT, SGPT)	X	X	X
	Alkaline phosphatase	X	X	X
	Gammaglutamyl transferase (GGT)	X	X	X
	Lactate dehydrogenase	X	X	X
	Amylase	X	X	X
	Lipase	X	X	X
Substrates	Glucose (plasma)	X	-	-
	Creatinine	X	X	X
	eGFR, calculated from serum creatinine using CKD-EPI formula	X	X	X
	Bilirubin, total	X	X	X
	Bilirubin, direct	X	X	X
	Cholesterol, total	X	X	X
	Triglycerides	X	X	X
	C-reactive protein	X	X	X
	Urea	X	X	X
Electrolytes	Calcium	X	X	X
Licetrorytes	Sodium	X	X	X
	Potassium	X	X	X
	Chloride	X	X	X
**		X		
Hormones	·			
* From urine collection	Urine potassium	-	X	-
cf. Flow Chart	Urine sodium	-	X	-
	Urine chloride	-	X	-
	Urine creatinine	-	X	-
	Potassium-creatinine-quotient	-	X	-
	Sodium-creatinine-quotient	-	X	-

c15848749-03

Page 51 of 84

Proprietary confidential information © 2018 Boehringer Ingelheim International GmbH or one or more of its affiliated companies

Table 5.2.3: 1 Routine laboratory tests (cont'd)

Category	Test name	\mathbf{A}^{1}	B^2	C^3
24h collection Urine	Urine potassium	-	X	-
	Urine sodium	-	X	-
	Urine chloride	-	X	-
	Urine creatinine	-	X	-
	Urine-aldosterone	-	X	-
Urinalysis (Stix)	Urine nitrite	X	X	X
[Urin-Sediment will be	Urine protein	X	X	X
performed, if urinalysis	Urine glucose	X	X	X
abnormal]	Urine ketone	X	X	X
	Urobilinogen	X	X	X
	Urine bilirubin	X	X	X
	Urine RBC	X	X	X
	Urine WBC	X	X	X
	Urine pH	X	X	X
Urine sediment	Only positive findings will be reported (for			
(microscopic	instance, the presence of sediment bacteria,			
examination if	casts in sediment, squamous epithelial cells,			
erythrocytes, leukocytes	erythrocytes, leukocytes)			
nitrite or protein are				
abnormal in urine)				

¹A: parameters to be determined at screening examination

The tests listed in Table 5.2.3: 2 are exclusionary laboratory tests which may be repeated as required. The results will not be entered in the CRF/database and will not be reported in the CTR. It is planned to perform these tests during screening only. Drug screening will be performed at screening and on Day 1.

²B: parameters to be determined during the study (for time points refer to Flow Chart)

³C: parameters to be determined during the Follow-up-examination

^{*} Urine collection fractions will be stored intermittent in a refrigerator. All collected fractions (0-24h) will be mixed for the 24h urine electrolyte measurement (intervals from 12:00-24:00, 108:00-120:00,180:00-192:00h will only be used for urine electrolytes not PK). Mixing should be done by transferring the entire content of all collection containers into a single PE/PP or glass container, and stirring the mixed fractions for about 1 min (manually or using a stir bar or other stirring device out of PE, PP, Teflon or glass).

c15848749-03 Page 52 of 84 Proprietary confidential information © 2018 Boehringer Ingelheim International GmbH or one or more of its affiliated companies

Table 5.2.3: 2 Exclusionary laboratory tests

Functional lab group	Test name		
Drug screening (urine)	Amphetamine/MDA		
2 rag servening (winter)	Barbiturates		
	Benzodiazepine		
	Cannabis		
	Cocaine		
	Methadone		
	Methamphetamines/MDMA/XTC		
	Opiates		
	Phencyclidine		
	Tricyclic antidepressants		
Infectious serology (blood)	Hepatitis B surface antigen (qualitative)		
	Hepatitis B core antibody (qualitative)		
	Hepatitis C antibodies (qualitative)		
	HIV-1 and HIV-2 antibody/p24-antigen (qualitative)		

To encourage compliance with alcoholic restrictions, a breath alcohol test (Alcotest[®] 7410, Dräger AG, Lübeck, Germany) will be performed as indicated in the Flow Chart and may be repeated at any time during the study at the discretion of an investigator or designee. The results will not be included in the CTR.

The laboratory tests listed in Table 5.2.3: 1 and 5.2.3: 2 will be performed at Medizinisches Versorgungszentrum [name], [name] & Partner, Kaiserslautern, Germany with the exception of drug screening tests. These tests will be performed at the trial site using Multidrogen Pipettiertest (Urin) (Diagnostik Nord GmbH, Schwerin, Germany).

Laboratory data will be transmitted electronically from the laboratory to the trial site.

5.2.4 Electrocardiogram

5.2.4.1 12-lead resting ECG

Recording

Twelve-lead resting ECGs (I, II, III, aVR, aVL, aVF, V1 - V6) will be recorded using a computerised electrocardiograph (CardioSoft EKG System, GE Medical Systems, Freiburg, Germany) at the time points given in the Flow Chart. Electrode placement will be performed according to the method of Wilson, Goldberger and Einthoven modified by Mason and Likar (hips and shoulders instead of ankles and wrists). Precise electrode placement will be marked with an indelible mark on the skin to allow reproducible placement throughout the study.

To achieve a stable heart rate at rest and to assure high quality recordings, the site personnel will be instructed to assure a relaxed and quiet environment so that all subjects are at complete rest.

All ECGs will be recorded for a 10 sec duration after subjects have rested for at least 5 min in a supine position. ECG recording will always precede all other study procedures scheduled for the same time (except for blood drawing from an intravenous cannula that is already in place) to avoid compromising ECG quality.

Boehringer Ingelheim BI Trial No.: 1399-0002 c15848749-03

04 Jul 2018

Trial Protocol

Page 53 of 84

Proprietary confidential information © 2018 Boehringer Ingelheim International GmbH or one or more of its affiliated companies

ECGs will be recorded as single ECGs or as triplicate ECGs (i.e. three single ECGs recorded within 180 sec) as indicated in the Flow Chart. Three triple ECGs will be recorded at baseline as indicated in the Flow Chart.

ECGs may be repeated for quality reasons for instance due to alternating current artefacts, muscle movements, or electrode dislocation. For repetition within triplicate ECGs the time window of 180 sec applies as well. The repeat ECGs are assigned to the respective scheduled time point. All ECG recordings including the repeat ECGs will be sent to the ECG core lab. The central ECG lab will select the ECGs with the best quality at each time point.

Trial Protocol

Page 54 of 84

Proprietary confidential information © 2018 Boehringer Ingelheim International GmbH or one or more of its affiliated companies

Abnormal findings, irrespective of whether they originate from central or local evaluation, will be reported as AEs (during the trial) or baseline conditions (at screening) if judged clinically relevant by the investigator.

Any ECG abnormalities will be monitored carefully and, if necessary, the subject will be removed from the trial and will receive the appropriate medical treatment.

5.2.5 Assessment of other safety parameters

5.2.5.1 Vital signs

Systolic and diastolic blood pressures (BP) as well as pulse rate (PR) or heart rate (heart rate is considered to be equal to pulse rate) will be measured by a blood pressure monitor (e.g. Dash 3000, GE Medical Systems, Freiburg, Germany) at the times indicated in the Flow Chart, after subjects have rested for at least 5 min in a supine position. All recordings should be made using the same type of blood pressure recording instrument on the same arm if possible.

5.2.5.2 Medical examinations

At screening, the medical examination will include demographics including height and body weight, smoking and alcohol history, relevant medical history and concomitant therapy, review of inclusion and exclusion criteria, review of vital signs (BP, PR), 12-lead ECG, laboratory tests, and a physical examination. At the end of trial examination, it will include review of vital signs, 12-lead ECG, laboratory tests, and a physical examination.

5.2.5.3 Spirometry

Functional FEV1 (Forced expiratory volume in 1 second), FEF25-75 (Forced expiratory flow) and FVC (Forced vital capacity) will be measured with a diagnostic system (e.g FlowScreen® or MasterScope). Measurements will be taken with the subject in seated position and carried out by an observer (It is preferable that the same trained individual performs the measurements for a given subject). The best of three efforts will be defined as the highest FEV1 and the highest FVC each obtained on any of three blows meeting the ATS criteria (with a maximum of eight attempts). The highest FEV1, FVC and best FEF25-75

Boehringer Ingelheim BI Trial No.: 1399-0002 c15848749-03

04 Jul 2018

Trial Protocol

Page 55 of 84

Proprietary confidential information © 2018 Boehringer Ingelheim International GmbH or one or more of its affiliated companies

(taken from the blow with the largest sum of FEV1 and FEV) will be selected regardless of whether they come from different spirometric manoeuvres or from the same manoeuvre (Refer to Flow Chart for time points). Equipment and techniques should conform to American Thoracic Society (ATS) criteria [P05-12782].

Abnormal findings will be recorded as AEs if judged clinically relevant by the investigator.

5.4 APPROPRIATENESS OF MEASUREMENTS

All measurements performed during this trial are standard measurements and will be performed in order to monitor subjects' safety and to determine pharmacokinetic parameters

Trial Protocol Page 56 of 84

Proprietary confidential information © 2018 Boehringer Ingelheim International GmbH or one or more of its affiliated companies

in an appropriate way. The scheduled measurements will allow monitoring of changes in vital signs, standard laboratory values, and ECG parameters that might occur as a result of administration of trial medication. The safety assessments are standard, are accepted for evaluation of safety and tolerability of an inhalative administered drug, and are widely used in clinical trials. The pharmacokinetic parameters and measurements outlined in Section 5.5 are generally used for assessments of drug exposure.

5.5 DRUG CONCENTRATION MEASUREMENTS AND PHARMACOKINETICS

Date and clock time of drug administration and pharmacokinetic sampling will be recorded in the CRFs.

PK sampling times and periods may be adapted during the trial based on information obtained during trial conduct including addition of samples and visits as long as the total blood volume taken per subject does not exceed 500 mL. Such changes would be implemented via non-substantial CTP Amendments.

5.5.1 Pharmacokinetic endpoints

The following pharmacokinetic parameters will be determined if feasible:

5.5.1.1 Secondary endpoints

After the first dose:

- AUC_{τ ,1} (area under the concentration-time curve of the analyte in plasma over a uniform dosing interval τ after administration of the first dose)
- C_{max} (maximum measured concentration of the analyte inplasma)

After the last dose:

- AUC_{τ ,ss} (area under the concentration-time curve of the analyte in plasma at steady state over a uniform dosing interval τ)
- $C_{max,ss}$ (maximum measured concentration of the analyte in plasma at steady state over a uniform dosing interval τ)

Boehringer Ingelheim BI Trial No.: 1399-0002

c15848749-03

04 Jul 2018

Page 57 of 84

Proprietary confidential information © 2018 Boehringer Ingelheim International GmbH or one or more of its affiliated companies

Trial Protocol

Boehringer Ingelheim BI Trial No.: 1399-0002 c15848749-03

04 Jul 2018

Trial Protocol Page 58 of 84

Proprietary confidential information © 2018 Boehringer Ingelheim International GmbH or one or more of its affiliated companies

5.5.2 Methods of sample collection

5.5.2.1 Plasma sampling for pharmacokinetic analysis

For quantification of analyte plasma concentrations, 3 mL of blood will be taken from an antecubital or forearm vein into a K2-EDTA (dipotassium ethylenediaminetetraacetic acid)-anticoagulant blood drawing tube (e.g. K2-EDTA BD Vacutainer®, Item no. 368856) at the times indicated in the Flow Chart. Blood will be withdrawn by means of either an indwelling venous catheter or by venipuncture with a metal needle.

The EDTA-anticoagulated blood samples will be centrifuged for about 10 min at about 2000 g to 4000 g and at 4 to 8°C. Two plasma aliquots will be obtained and stored in polypropylene tubes. The first aliquot should contain at least 0.7 mL plasma. The process from blood collection until transfer of plasma aliquots into the freezer should be completed within 90 min. For each aliquot the time when the sample was placed in the freezer will be documented. Until transfer on dry ice to the analytical laboratory, the aliquots will be stored upright at about -20°C or below at the trial site. The second aliquot will be transferred to the analytical laboratory after the bioanalyst has acknowledged safe arrival of the first aliquot. At the analytical laboratory the plasma samples will be stored at about -20°C or below until analysis.

Boehringer Ingelheim BI Trial No.: 1399-0002 c15848749-03

04 Jul 2018

Trial Protocol

Page 59 of 84

Proprietary confidential information © 2018 Boehringer Ingelheim International GmbH or one or more of its affiliated companies

At a minimum, the sample tube labels should list the following information: BI trial number, subject number, visit, and planned sampling time. Further information such as matrix and analyte may also be provided.

After completion of the trial the plasma samples may be used for further methodological investigations,

The study samples will be discarded after completion of the additional investigations but not later than 5 years upon the final study report has been signed.

04 Jul 2018

c15848749-03 Trial Protocol

Proprietary confidential information © 2018 Boehringer Ingelheim International GmbH or one or more of its affiliated companies

Page 60 of 84

5.5.3 Analytical determinations

5.5.3.1 Analytical determination of analyte plasma concentration

BI 1265162 concentrations in plasma will be determined by a validated LC-MS/MS (liquid chromatography tandem mass spectrometry) assay. The analysis will be performed at Drug Metabolism and Pharmacokinetics Germany, Boehringer Ingelheim Pharma GmbH & Co KG, Biberach, Germany. All details of the analytical method will be available prior to the start of sample analysis.

As described in Section 4.1.5, the bioanalyst may be unblinded during sample analysis.

5.6 BIOMARKER

Not applicable.

Boehringer Ingelheim BI Trial No.: 1399-0002

04 Jul 2018

Proprietary confidential information © 2018 Boehringer Ingelheim International GmbH or one or more of its affiliated companies

Trial Protocol

5.7 PHARMACODYNAMICS

Not applicable.

c15848749-03

5.8 PHARMACOKINETIC - PHARMACODYNAMIC RELATIONSHIP

Not applicable.

Page 61 of 84

c15848749-03

Page 62 of 84

Proprietary confidential information © 2018 Boehringer Ingelheim International GmbH or one or more of its affiliated companies

6. INVESTIGATIONAL PLAN

6.1 VISIT SCHEDULE

Exact times of measurements outside the permitted time windows will be documented. The acceptable time windows for screening and end of trial examination are given in the Flow Chart.

Study measurements and assessments scheduled to occur 'before' trial medication administration on Days 1 and 8 are to be performed and completed within a 3 h-period prior to the trial drug administration (including blank values for PK).

The acceptable deviation from the scheduled time for vital signs, spirometry, ECG and laboratory tests will be \pm 30 min for the first 4 h after trial drug administration and \pm 45 min thereafter.

If scheduled in the Flow Chart at the same time as a meal, blood sampling, vital signs and 12-lead ECG recordings have to be done first. Furthermore, if several measurements including venipuncture are scheduled for the same time, venipuncture should be the last of the measurements (if at the same time point as spirometry, spirometry should be last measurement) due to its inconvenience to the subject and possible influence on physiological parameters.

For planned individual plasma concentration sampling times and refer to the Flow Chart. While these nominal times should be adhered to as closely as possible, the actual sampling times will be recorded and used for determination of pharmacokinetic parameters.

If a subject misses an appointment, it will be rescheduled if possible. The relevance of measurements outside the permitted time windows will be assessed no later than at the Blinded Report Planning Meeting.

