7.3 PLANNED ANALYSES

Adherence to the protocol (such as inclusion/exclusion criteria, times of measurement, compliance with intake of trial medication, treatment dispensing errors, prohibited concomitant medication, completeness and consistency of data) will be checked. Important protocol violations (IPVs) will be identified no later than in the Report Planning Meeting and provided in the TSAP.

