7.3.3 Safety analyses

Safety will be assessed for the endpoints and parameters of interest listed in Section 5.2.1. All treated subjects (that is, all subjects who received at least one dose of study drug), will be included in the safety analysis. Safety analyses will be descriptive in nature and will be based on BI standards.

Treatments will be compared in a descriptive way. The placebo control group in the safety evaluation will consist of all placebo treated subjects, regardless of the dose group in which they were treated. The active treatment groups will be compared to the placebo group in a descriptive way. Tabulations of frequencies/proportions will be used for the evaluation of categorical (qualitative) data, and tabulations of descriptive statistics will be used to analyse continuous (quantitative) data.

The analyses will be done by 'treatment at onset'.

Measurements (such as ECG, vital signs, or laboratory parameters) or AEs will be assigned to treatments (see Section 4.1) based on the actual treatment at the planned time of the measurement or on the recorded time of AE onset (concept of treatment emergent AEs). Therefore, measurements planned or AEs recorded prior to first intake of trial medication will be assigned to 'screening', those between first trial medication intake until end of the residual effect period (see Section 5.2.2.2) will be assigned to the treatment period. Events after the residual effect period but prior trial termination date will be summarized as 'follow-up'. These assignments including the corresponding time intervals will be defined in detail in the TSAP. Please note that AEs occurring after the last per protocol contact but entered before database lock will be reported to drug safety only and will not be captured in the trial database.

Additionally, further treatment intervals (analysing treatments) may be defined in order to provide summary statistics for time intervals, such as combined treatments, on-treatment totals or periods without treatment effects (such as screening and follow-up).

Adverse events will be coded using the Medical Dictionary for Regulatory Activities (MedDRA). Frequency, severity and causal relationship of AEs will be tabulated by treatment, system organ class and preferred term. SAEs, AESIs (see Section 5.2.2.1) and other significant AEs (according to ICH E3) will be listed separately.

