6.2 IMPORTANT PROTOCOL DEVIATIONS

Data discrepancies and deviations from the CTP will be identified for all patients entered and randomised who did not fail during screening.

Consistency check listings (for identification of deviations from time windows) and a list of protocol deviations (e.g. deviations in drug administration, in blood sampling times, etc.) will be provided to be discussed at the report planning and database lock meeting (RPM/DBLM). At this meeting, it will be decided whether a discrepant data value can be used in analyses or whether it must be corrected in the clinical database. Each protocol deviation must be assessed to determine whether it is an important protocol deviation (iPD). For definition of iPDs, and for the process of identification of these, refer to the Boehringer Ingelheim (BI) SOP "Integrated Quality and Risk Management Process" ([2](#)).

If any iPDs are identified, they are to be summarised into categories and will be captured in the RPM/DBLM minutes via an accompanying excel spreadsheet. The table below contains the categories which are considered to be iPDs in this trial. If the data show other important PDs, this table will be supplemented accordingly by the time of the RPM/DBLM.

iPDs will be summarised and listed.

Table 6.2: 1 Important protocol deviations

Category / Code	Description
A	Entrance criteria not met
A1	Inclusion criteria violated
A2	Exclusion criteria violated
B	Informed consent
B1	Informed consent not available
B2	Informed consent too late
C	Trial medication and randomisation
C1	Incorrect trial medication taken
C2	Randomisation not followed
C3	Non-compliance
C4	Incorrect intake of trial medication
C5	Incorrect dose of trial medication taken
D	Concomitant medication
D1	Prohibited medication use
E	Missing data
	None ¹
G	Other trial specific important deviation
G1	Certain deviations of procedures used to measure secondary PK data

Deviations C1, C2, C5 and G1 can only be detected at the trial site.

¹ Missing visits, evaluations, and tests will be considered missing data, not protocol deviations

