6.7 BASELINE, TIME WINDOWS AND CALCULATED VISITS

There will be a centralised evaluation of 12-lead ECG recordings at the time points specified in [Table 6.7: 1](#).

Triple ECGs will be recorded at Visit 2 assessments and will be evaluated by a central lab. At Visit 1 and 3 only single ECGs will be recorded. This data will not be evaluated centrally. At predose (Visit 2, Day 1, planned time point -01:30, notation for data transfer -01:30, -01:25, and -01:20), three triplicate ECGs (9 single ECGs) will be recorded.

For all on-treatment assessments as well as for the 3 predose triplicates, only the first of the 3 replicate ECGs at a single assessment time will be evaluated centrally.

The baseline value of an ECG variable is defined as the mean of the first single ECG measurement of each triple ECG prior to first drug administration.

Table 6.7: 1 Time schedule of 12-lead ECG recordings with centralised evaluation

Visit	Day	Planned time [hh:mm] - relative to respective drug administration	Study phase
2	1	-01:30	Baseline
		00:10	On-treatment
		01:00	
		04:00	
		12:00	
	2	24:10	
	3	48:10	
	5	96:10	
	6	120:10	
	8	164:30	
		168:10	
		169:00	
		172:00	
		180:00	
	9	191:30	

For urine electrolytes there is a whole baseline day to have time matched baseline measurements (see [Table 6.7: 2](#) for details).

In all other analyses the last non-missing value determined prior to the first dosing of BI 1265162 will be defined as baseline.

Time windows are defined in Section 6.1 of the CTP. Adherence to time windows will be checked at the RPM/DBLM.

Unscheduled measurements of laboratory data, vital signs or spirometry data will be assumed to be repeat measurements of the most recent scheduled measurement (e.g. for follow-up or confirmation of a particular value). Therefore, unscheduled measurements will be assigned to the planned time point of the previous scheduled measurement.

Table 6.7: 2 Time schedule of urine electrolyte measurements

Visit	Day	Planned time interval [hh:mm] - relative to respective drug administration (planned time at the day)	Study phase
2	-1	-24:00 to -20:00 (08:00 to 12:00)	Baseline
		-20:00 to -16:00 (12:00 to 16:00)	
		-16:00 to -12:00 (16:00 to 20:00)	
		-12:00 to 00:00 (20:00 to 08:00 on Day 1)	
	5	96:00 to 100:00 (08:00 to 12:00)	On-treatment
		100:00 to 104:00 (12:00 to 16:00)	
		104:00 to 108:00 (16:00 to 20:00)	
		108:00 to 120:00 (20:00 to 08:00 on Day 6)	
	8	168:00 to 172:00 (08:00 to 12:00)	
		172:00 to 176:00 (12:00 to 16:00)	

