		176:00 to 180:00 (16:00 to 20:00)	
		180:00 to 192:00 (20:00 to 08:00 on Day 9)	

Descriptive statistics of laboratory data will be calculated by planned time point based on the worst value of the subject at that planned time point (or assigned to that planned time point).

For vital signs and spirometry, descriptive statistics will be calculated by planned time point based on the last value of the subject at that planned time point (or assigned to that planned time point).

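### The ±30 min window in Protocol 6.1 exceeds the 10, 15 and 20 min post-dose times it governs, and no visible rule marks in-window lateness in the vital-sign and spirometry summaries

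*Protocol*

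**What the plan says.** The Flow Chart plans ECG and vital signs 10 min after dosing on Days 1, 2, 3, 6 and 8, and 15 min after dosing on Day 5. It plans spirometry 20 min after dosing on Days 1 and 8.

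Protocol 6.1 gives these measurements, with laboratory tests, one tolerance: plus or minus "30 min for the first 4 h after trial drug administration", and ±45 min later on. No visible footnote or section sets a tighter limit for the early readings.

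On recording, the same section says "Exact times of measurements outside the permitted time windows will be documented". For plasma samples it says "the actual sampling times will be recorded and used for determination of pharmacokinetic parameters". It makes no such statement for in-window vital signs, spirometry or ECG.

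SAP 6.7 adds no window of its own: "Time windows are defined in Section 6.1 of the CTP". It then states: "For vital signs and spirometry, descriptive statistics will be calculated by planned time point". The time-deviation flags in SAP 7.5.2 concern plasma concentrations.

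**The concern.** A tolerance of 30 min is unremarkable for a 2-h or 4-h reading. For a 10-min reading it is three times the planned delay. A blood pressure, pulse or FEV1 value taken at 40 or 50 min can enter the tables as a 10-min or 20-min value and count as fully compliant.

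The early readings are there to describe what happens shortly after inhalation. Protocol 2.3 regards 10 min as usually long enough to see acute effects of an inhaled drug. It says this to justify the spacing between subjects, not a measurement window, but it shows what the protocol takes the acute period to be. On Days 1 and 8 the plasma schedule also divides the first hour finely (2, 5, 10, 15, 20, 40 and 60 min). At stake is whether the early rows of the vital-sign and spirometry tables describe the time in their label.

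**Working it through.** No figure in the plan has to be reproduced. The check is window arithmetic.

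**Inputs.** Tolerance 30 min (Protocol 6.1). Planned times: Flow Chart. Limits = planned time ± 30 min.

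| Reading | Planned (min) | Lower limit (min) | Upper limit (min) |
|---|---|---|---|
| Vital signs, ECG; Days 1, 2, 3, 6, 8 | 10 | 10 − 30 = −20 | 10 + 30 = 40 |
| Vital signs, ECG; Day 5 | 15 | 15 − 30 = −15 | 15 + 30 = 45 |
| Spirometry; Days 1, 8 | 20 | 20 − 30 = −10 | 20 + 30 = 50 |

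Read literally, every lower limit falls before dosing.

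**Overlap.** The 1-h vital-sign window on Days 1 and 8 is 60 ± 30 = 30 to 90 min. It shares 30 to 40 min, that is 10 min, with the 10-min window. A shared elapsed time needs the first reading to be at least 30 − 10 = 20 min late and the second at least 60 − 40 = 20 min early. The 2-h spirometry window starts at 120 − 30 = 90 min, after 50 min, so spirometry windows do not overlap.

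**How many times are early.**
- Vital signs on treatment: 0:10, 1:00, 4:00, 12:00, 24:10, 48:10, 96:15, 120:10, 164:30 (as printed), 168:10, 169:00, 172:00, 180:00, 191:30. That is 14, of which 6 are early: 6/14 = 43%. Overlap arises at 2 of the 6.
- Spirometry on treatment: 0:20, 2:00, 100:00, 168:20, 170:00. That is 5, of which 2 are early: 2/5 = 40%.

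**A narrower limit.** If the 1-h window stays as it is, the vital-sign overlap disappears once the late allowance *w* satisfies 10 + *w* < 30, so *w* < 20 min. With *w* = 10 the upper limits become 20, 25 and 30 min.

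**Feasibility of that example at six actuations (600 µg).** Time zero is the first actuation (Protocol 4.1.4). Assumptions not in the documents: 0.5 to 1 min per actuation, 1 to 3 min to leave the dosing room, 1 min per spirometry attempt.
- ECG start: 3–6 (actuations) + 1–3 (move) + 5 (supine rest) = 9–14 min.
- Vital signs after a triplicate ECG of up to 3 min: 12–17 min, below 20 but possibly above 15.
- Spirometry begun at 20 min with the maximum of eight attempts: 20 + 8 = 28 min, below 30.

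This treats one subject in isolation. It leaves out the plasma draws at 2, 5, 10 and 15 min on Days 1 and 8, and dosing of successive subjects that may be only 10 min apart (Protocol 2.3). The real margin is therefore unknown.

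**Two printed times.**
- Day 5 ECG: 96:15 in the Flow Chart, 96:10 in SAP Table 6.7: 1.
- Day 8 pre-dose: 164:30 in both documents, beside clock time 06:30 in the Flow Chart. With 168:00 = 08:00, 06:30 corresponds to 166:30. As printed, 168:00 − 164:30 = 3.5 h, outside the 3-h pre-dose limit of Protocol 6.1. The clock-time reading gives 1.5 h, inside it.

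**The case against.** The strongest reply is that other text already limits lateness. At 0:10, 96:15 and 168:10 a plasma sample is planned with the ECG and vital signs. Sample times are to be kept as near nominal as possible, and Protocol 6.1 puts venipuncture last. Where venipuncture is used, a vital-sign reading at 40 min would break that order. This stands in part, and it covers both overlap days. But Protocol 5.5.2.1 also allows an indwelling catheter, Days 2, 3 and 6 have no plasma sample at the 10-min time, and spirometry is placed after the blood draw, so the rule sets it no upper limit.

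Second, acute safety does not rest on these tables. Changes judged clinically relevant become adverse events with their own onset time. This stands and caps the importance of the point.

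Third, the gap is partly an argument from silence. A reader might infer that actual times will not exist. The documents do not support that. The protocol checks "Adherence to the protocol (such as inclusion/exclusion criteria, times of measurement", the SAP provides "Consistency check listings (for identification of deviations from time windows", individual values are listed (SAP 7), and blinding ECG readers to recording time (Protocol 4.1.5.1) implies that those times are held. The CRF and the ADS Plan are not available here. What can be said is narrower: the visible checks target deviations from the window, and a 40-min reading is not one.

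A reader might also cite Protocol 7.3.3, where measurements are assigned "based on the actual treatment at the planned time of the measurement". That sentence assigns readings to treatments and phases, not to time-point rows. Only SAP 6.7 supports the planned-time step.

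**Conclusion.** The point holds as a modest one about descriptive acute-safety data, and the change is worth making. The stated rule lets vital signs planned at 10 or 15 min be taken up to 40 or 45 min, and spirometry planned at 20 min up to 50 min, and still be summarised under the planned time. On Days 1 and 8 the 10-min and 1-h vital-sign rows can hold readings from the same elapsed time.

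Three stronger readings are not supported:
- That an acute effect will be missed. The documents show no known effect that disappears between 10 and 40 min. The primary endpoint counts subjects with drug-related adverse events, and the escalation stopping rules rest on adverse events, QT and potassium; none uses the planned-time summaries.
- That 43% and 40% measure bias. They count schedule times, and how late readings would be in practice is unknown.
- That ECG summaries are distorted. Most of SAP 7.8.4 is not visible, so no claim is made about them.

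The conclusion assumes that no removed footnote or section narrows the window.

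**What to change.** In Protocol 6.1, set a separate window for vital signs, spirometry and ECG planned within 20 min of dosing. It should lie entirely after dosing and not overlap the window of the next planned time. Agree its width with the site, considering up to six actuations, the separate dosing room, 5 min supine rest, the early plasma draws and staggered dosing. About 10 min after the planned time is only an example, because its feasibility rests on the assumed times above. State that actual times are recorded for these readings.

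In SAP 6.7, list actual elapsed time since dosing for the same readings and flag in the time-point summaries those outside the narrower window.

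Separately, reconcile the Day 5 ECG time (96:15 against 96:10) and the Day 8 pre-dose time (164:30 against clock time 06:30) across both documents. These are corrections of record and add nothing to the weight of the main point.

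The cost is protocol and SAP wording, plus a few more recorded time deviations, most likely at 600 µg, where six actuations are needed.
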